10.3.2 Primary efficacy outcome

One null-hypothesis as outlined in section 10.1 will be tested in the confirmatory analysis.

Absolute values and changes from first baseline and follow ups respectively will be presented for the Berg Balance Scale after 3 months of treatment using descriptive summary statistics for each treatment period. Moreover, percentage changes from baseline and follow ups respectively will be displayed.

The confirmatory inferential statistical evaluation of the primary outcome measure will be based on a linear mixed effects model with the Berg Balance Scale as dependent variable. This model will use the treatment group and period as fixed factor and the first baseline Berg Balance Scale as covariate. Random patient effects will be introduced for the intercepts and thus taking the correlation within patients into account.

ottobock.	CLINICAL INVESTIGATION PLAN	Document number:	PD-PS00120016A-001
		Version number:	7
Project name	Clinical trial comparing C-Brace to KAFO/SCO	Project no.	PS00120016A

The confirmatory analysis of the primary efficacy endpoint will be done for the intention-to-treat population. Additional efficacy analyses will be conducted for the per-protocol population. The p-values of these analyses will be interpreted in the exploratory sense only.

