10.3.1 Secondary outcome analysis

Analyses for the secondary outcome measures will be performed for the intention-to-treat population as well as for the per-protocol population. All inferential analyses for the secondary efficacy variables will be interpreted in the exploratory sense. All secondary outcome measures will be evaluated by using descriptive statistics primarily, absolute values at each time point and if appropriate changes from first baseline and follow ups respectively. These analyses will be performed in a similar way as the primary efficacy outcome using a linear mixed effects model when appropriate.

Additional attention will be paid to the exploration of the measurements of safety and falls. The number of Falls is expected to be reduced in general by using a C-Brace, but the extent of a possible reduction remains uncertain. Therefore, frequency of falls, severity of falls, fall-related injuries, fear of falling and related treatment efforts will be explored in rigorously in order to formulate appropriate hypothesis for future research.

In the past the reduced probability of falling more than once by using C-Brace compared to KAFO / SCO showed the most promise as a reliable measure to compare the two device types, since it was less sensitive to outliers e.g. patients with a high number of falls on either device as compared to the total number of falls. However, sample sizes in prior research were relatively small and estimations for potential differences remain uncertain, albeit of great clinical interest.

Therefore, we explore whether a reduction in the probability of falling more than once using the C-Brace can be detected by a McNemar Test for paired proportions. This test will likely be underpowered in comparison to the expected best-case scenario used in the sample size calculation and will be reported accordingly.

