10.4 Interim analysis

An interim analysis will be performed after at least 35 patients have completed the study. After the interim analysis, it will be decided whether: 1) the sample size must be increased 2) the study will be

ottobock.	CLINICAL INVESTIGATION PLAN	Document number:	PD-PS00120016A-001
		Version number:	7
Project name	Clinical trial comparing C-Brace to KAFO/SCO	Project no.	PS00120016A

stopped early for futility, or 3) interim hypothesis testing will be done for the primary objective and select secondary objectives.

The interim analysis will be performed for the primary endpoint (BBS). A statistical power calculation will be performed based on the observed intraindividual changes (IIC) between C-Brace and KAFO arms. The following rules will be applied:

1. If the power based on observed mean and standard deviation for the BBS IIC for the intended target of 56 subjects is less than 0.9, the proposed sample size for the study may be increased.
2. If the observed mean IIC is less than 3, the study may be stopped for futility, since this difference is of no clinical relevance.
3. If the power based on observed mean and standard deviation for the BBS IIC with the interim analysis cohort of at least 35 subjects is greater than 0.95, hypothesis testing will be performed at the $\alpha = 0.02$ level to determine statistical significance. In this case, the primary objective will be analyzed at the 0.03 level for the final analysis of the full study cohort at the completion of the study to maintain an overall Type I error rate of 5%. If the power is less than 0.95, hypothesis testing will only be performed at the conclusion of the study and statistical significance determined using $\alpha = 0.05$.

Conditional hypothesis testing may be performed for select secondary objectives using the same method described in rule 3 above.

ottobock.	CLINICAL INVESTIGATION PLAN	Document number:	PD-PS00120016A-001
		Version number:	7
Project name	Clinical trial comparing C-Brace to KAFO/SCO	Project no.	PS00120016A

11 Risk and benefit of the investigation device and clinical investigation

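### Section 10.4 lets unnamed secondary objectives be tested for significance at rule 3's alpha levels, although the plan makes all secondary inference exploratory and controls nothing across objectives

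*Combined protocol and SAP*

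**What the plan says.** Section 10.4 plans an interim analysis once at least 35 patients have completed, and introduces it as an analysis of the primary endpoint. Its third possible outcome is nevertheless that "interim hypothesis testing will be done for the primary objective and select secondary objectives".

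Rule 3 is written for the intraindividual change in BBS. It applies when the power computed from the observed mean and standard deviation "with the interim analysis cohort of at least 35 subjects is greater than 0.95". In that case "hypothesis testing will be performed at the $\alpha = 0.02$ level to determine statistical significance", and "the primary objective will be analyzed at the 0.03 level for the final analysis", "to maintain an overall Type I error rate of 5" per cent. If the power is lower, there is one test at the end, at 0.05. The section then closes with "Conditional hypothesis testing may be performed for select secondary objectives using the same method described in rule 3 above".

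The analysis sections say something different. Section 10.3.2 (Primary efficacy outcome): "One null-hypothesis as outlined in section 10.1 will be tested in the confirmatory analysis". Section 10.3.1 (Secondary outcome analysis): "All inferential analyses for the secondary efficacy variables will be interpreted in the exploratory sense". Section 6.1.2 lists seven secondary objectives, and section 10.4 singles out none of them.

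**The concern.** Splitting alpha between an interim and a final look serves a formal claim of significance, and an exploratory analysis has no need of it. Section 10.4 offers that machinery to secondary objectives it does not identify. It gives no criterion for choosing them, no requirement that BBS be rejected first, and no adjustment for their number. Testing is also optional, so nothing stops the choice from being made after the interim data have been seen.

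At stake is the status of the secondary results. A report could present a secondary outcome as significant under a prespecified alpha rule, although elsewhere the plan allows only exploratory reading. Many candidate outcomes are self-reported and the trial is open-label, so the strength claimed for them matters.

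**Working it through.** **1. The plan's own figure.** 0.02 + 0.03 = 0.05, so the stated 5% reproduces as a Bonferroni split over two looks at one endpoint. A simulation of rule 3 for one null endpoint (40,000 trials, looks at n = 35 and 56, one-sided) rejected in 0.0499 of trials with power computed at alpha 0.02, and in 0.0509 at alpha 0.05. The simulation error is √(0.05 × 0.95 / 40,000) = 0.0011, so both agree with 0.05. The split has no term for the number of endpoints.

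**2. What the power condition means.** With n fixed, power computed from the observed mean and SD depends only on t = mean/(SD/√n). Setting noncentral-t power to 0.95 at n = 35, one-sided:

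- Power at alpha 0.05: d = 0.5675, t = 0.5675 × √35 = 3.36, one-sided p = 0.00097.
- Power at alpha 0.02: d = 0.6456, t = 0.6456 × √35 = 3.82, one-sided p = 0.00027.

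Section 10.4 gives neither the alpha nor the sidedness for this calculation. Two-sided versions need a larger t (3.71 and 4.14), so 0.00097 is the loosest case. If the condition is applied to each objective's own data, any objective that meets it is already significant at 0.02.

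**3. False interim claims, condition applied to each objective's own effect.** For 20 independent nulls:

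- 1 − (1 − 0.00097)^20 = 0.019
- 1 − (1 − 0.00027)^20 = 0.005

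For 7 independent nulls the simulation gave 0.0075 and 0.002.

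**4. Claims at the end of the study.** Under the null the condition is almost never met, so nearly every objective reaches the final test at 0.05:

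- 7 objectives, independent: 1 − 0.95^7 = 0.30 (simulation 0.30)
- 20 scores, independent: 1 − 0.95^20 = 0.64
- 7 objectives, assumed correlation 0.3: 0.25 (simulation)
- 7 objectives, assumed correlation 0.6: 0.18 (simulation)

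**5. Condition applied to BBS only.** If the BBS effect is real, meeting the condition says nothing about a null secondary objective, so the restraint in step 3 does not apply. Each tested objective would have 0.02 and, by extension from the primary, 0.03. That is at most 0.05 over both looks, so the totals for independent nulls are no higher than in step 4.

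**6. The counts.** Seven is the number of objectives in section 6.1.2. Twenty is a rounded-down count of scores from section 8.2.2: ABC, DGI, 6-minute walk, stair index up and down (5); fear of falling indoors and outdoors (2); RNL, EQ-5D-5L, WLQ, QUEST (4); OPUS domains (3); SF-36 concepts (8). That makes 22. It leaves out the falls measures and the two patient-related questions, which are asked only at visit 2.

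**7. Fit to the falls outcome.** Rule 3 works from a mean and an SD. Falling more than once, which sets N = 56, is a paired proportion tested by McNemar's test. Section 10.4 does not say how the method would carry over.

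**The case against.** The strongest reply is that section 10.3.1 already governs. It makes all secondary inference exploratory without an exception for the interim. Section 10.4 never calls a secondary test confirmatory, and it states the 5% only in connection with the primary objective. If the secondary interim tests are exploratory, no multiplicity control is needed. Part of this stands: a reader might infer that section 10.4 creates extra confirmatory hypotheses, and the text does not say so. But section 10.4 does not carry the exploratory label over either, and the method it lends to secondaries exists to determine significance at fixed alpha levels. That is a conflict between sections, beyond a missing detail.

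A reader might also infer that objectives will be picked because their own interim effects look best. The documents do not establish this. Rule 3's condition is written for BBS, and conditional testing could mean conditional on the BBS result. Both readings are open.

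A further tempting inference is a chance of about one in three of a false interim claim, from 1 − 0.98^20 = 0.33, or 0.46 from 1 − 0.97^20 at the 0.03 level. Where each objective must meet the power condition itself, both figures ignore that condition, and step 3 gives 0.019 or less. The 0.33 would need the condition to be met for reasons unrelated to the secondaries, and all 20 to be tested; the text supports neither assumption. The 0.03 level is stated only for the primary objective, and only after an interim test.

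Finally, unadjusted final p-values for all secondary outcomes arise under section 10.3.1 anyway, so deleting the sentence in 10.4 does not remove them. This stands. What section 10.4 adds is a basis for calling some of them significant, so the fix must also address labelling.

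**Conclusion.** The point holds as a conflict between section 10.4 and sections 10.1.1, 10.3.1 (Secondary outcome analysis) and 10.3.2, with no control across objectives. It should be fixed, but it does not touch the primary BBS analysis.

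The size depends on use. If each objective must meet the power condition itself, false interim claims are rare (about 0.02 or less for 20 independent nulls). The main exposure is a significance claim at the final 0.05 level: about 0.30 for 7 and 0.64 for 20 independent nulls, falling to 0.18 for 7 at correlation 0.6. These figures assume that every counted objective is null and is tested for a claim. The counts and correlations are illustrative, because the plan names no objectives. If all secondary p-values are in fact reported as exploratory, these are not error rates of any claim, and what remains is the conflicting text.

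**What to change.** Before the interim look, delete the last sentence of section 10.4 and the mention of secondary objectives in option 3. Add that all secondary p-values, interim and final, are exploratory under section 10.3.1 and carry no alpha-level claim of significance.

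If one or two secondary claims are wanted, name them now in a fixed order, to be tested only after the BBS null hypothesis is rejected, and state their levels and sidedness. All other secondary outcomes would get estimates and confidence intervals.

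The cost is a short amendment under section 15.3. No patient, visit or sample size changes. The sponsor gives up ad hoc secondary significance claims. Timing matters, because naming objectives after the interim data have been seen would not cure the problem.

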12.1 Description of possible adverse events & adverse device effects

Falls are expected to be reduced in general using a C-Brace, however in patients with limb impairment falls might occur.

12.2 Definitions

The investigator is responsible for recording all AEs diagnosed in the frame of study visits, reported by the participant or communicated to the investigator by a third person during the study period.

Adverse Event

An AE is (acc. to ISO 14155-2020) any untoward medical occurrence, unintended disease or injury, or untoward clinical sign (including abnormal laboratory findings) in patients, users or other persons, whether or not related to the investigational medical device

A Serious Adverse Event (SAE) is an Adverse Event that (acc. to ISO 14155-2020):

1. led to a death;
2. led to a serious deterioration in the health of the patient that
 - results in a life-threatening illness or injury;
 - results in a permanent impairment of a body structure or a body function;
 - requires hospitalization or prolongation of existing hospitalization;
 - results in medical or surgical intervention to prevent permanent impairment to body structure or a body function; or led to
3. fetal distress, fetal death or a congenital abnormality or birth defect. (Ref ISO/DIS 14155-2020)

Adverse Device Effects (ADE): adverse event related to the use of an investigational medical device. This includes adverse events resulting from insufficient or inadequate instructions for use, deployment, implantation, installation, or operation, or any malfunction of the investigational medical device, as well as, any event resulting from use error or from intentional misuse of the investigational medical device (Ref ISO/DIS 14155-2020).

ottobock.	CLINICAL INVESTIGATION PLAN	Document number:	PD-PS00120016A-001
		Version number:	7
Project name	Clinical trial comparing C-Brace to KAFO/SCO	Project no.	PS00120016A

Serious Adverse Device Effect (SADE): adverse device effect that has resulted in any of the consequences characteristic of a serious adverse event. (Ref ISO/DIS 14155-2020)

Unanticipated Serious Adverse Device Effect (USADE): serious adverse device effect, which by its nature, incidence, severity or outcome has not been identified in the current version of the risk analysis report (Ref ISO/DIS 14155-2020).

Device deficiency represents inadequacy of a medical device with respect to its identity, quality, durability, reliability, safety or performance. Device deficiencies include malfunctions, use errors, and inadequate labeling (Ref ISO/DIS 14155-2020).

12.2.1 Additional national definitions

Germany

Notwithstanding the definitions in ISO/DIS 14155-2020, the following definitions apply according to Medizinprodukte Sicherheitsplanverordnung (MPSV) and have to be used for categorization of AEs and SAEs in Germany:

According to §2 (5) MPSV a serious adverse event is "... any unintentional event occurring in a clinical trial or performance evaluation subject to authorization which has led, could have led or could lead directly or indirectly to the death or serious deterioration of the state of health of a subject, user or other person without taking into account whether the event was caused by the medical device; the foregoing applies mutatis mutandis to serious adverse events that have occurred in a clinical trial or performance evaluation for which an exemption from the licensing requirement pursuant to § 20 (1) sentence 2 of the "Medizinproduktegesetz" has been granted.

According to §2 (1) MPSV an event is "... a malfunction, a failure, a change in features or performance or an improper labelling or instructions for use of a medical device, which has led, could have led or could lead directly or indirectly to the death or serious deterioration of the state of health of a patient, user or other person; a malfunction is also considered to be a lack of fitness for use, which causes misuse."

Netherlands

Definitions for AE/SAE in the Netherlands follow the definitions in MEDDEV 2.7/3 rev.3 which are in line with the definitions in ISO 14155 2020. Therefore, no national definitions for AE/SAE are necessary.

United States of America

ottobock.	CLINICAL INVESTIGATION PLAN	Document number:	PD-PS00120016A-001
		Version number:	7
Project name	Clinical trial comparing C-Brace to KAFO/SCO	Project no.	PS00120016A

Definitions for AE/SAE in the US follow the definitions in ISO 14155. Therefore, no national definitions for AE/SAE are necessary.

Austria

Notwithstanding the definitions of ISO14155-2020, the following definition applies according to the Austrian "Medizinproduktegesetz":

Austria §2(17) MPG: Adverse Device Effect ("Nebenwirkung") is any undesirable clinical event occurring under and related to the normal conditions of use of a medical device, i.e., a device-related adverse event.

12.3 Documentation of Adverse Events / Serious Adverse Events

All AEs are to be recorded once only on the appropriate AE pages in the CRF. The investigator should complete all the details requested including dates of onset, severity, corrective therapies given, outcome and opinion as to whether the AE is likely to be device-related. Each event should be recorded separately.

In the case of a SAE, the investigator must complete, sign and date the SAE pages from the CRF, check that the data are consistent, and send a copy without any further delay to the contact specified below:

Ottobock SE & Co. KGaA, [name], [name]
[contact]

Where additional follow-up information is required, this should be completed on a SAE follow-up form, a copy sent to the Sponsor and the original placed in the SAE section of the CRF.

12.4 Reporting of Adverse Events / Adverse Device Effects

During the entire patient follow-up period, any AE or ADE that occurs to a person during the study period must be followed until it resolves or is deemed permanent. Any AE or ADE, regardless of whether it is related to the study, must be documented. Any SAE (device/procedure-related or not device/procedure-related) must be reported to the sponsor on the form provided for this purpose in the case report form without any further delay from the moment of occurrence (or as soon as the investigator becomes aware of it). The initial report may be followed by relevant additional information within 7 days.

In the case of SAE and SADE, sponsor and investigator together complete the reporting forms for Ethics Committee(s) and competent authority. Both sponsor and investigator evaluate the causal rela-

ottobock.	CLINICAL INVESTIGATION PLAN	Document number:	PD-PS00120016A-001
		Version number:	7
Project name	Clinical trial comparing C-Brace to KAFO/SCO	Project no.	PS00120016A

tionship between the AE and investigational device and if different note this on the form. After signing the forms, either sponsor or investigator forwards it to the Ethics Committee and regulatory authority, if applicable. In case of multicenter and/or multinational studies, the sponsor has responsibility to inform other centers and relevant Ethics Committees / authorities.

12.4.1 Additional national requirements for reporting of adverse events

Germany

Notwithstanding the definitions in ISO/DIS 14155-2011, the following definitions apply according to Medizinprodukte Sicherheitsplanverordnung (MPSV) and have to be used for reporting AEs and SAEs in Germany:

After the sponsor has received a notification of an SAE that cannot be ruled out as being related to the medical device under investigation, a reference product or the therapeutic or diagnostic measures applied in the clinical trial or the other conditions for conducting the clinical trial, this must be reported to the responsible competent authority (BfArM) without further delay. The following form must be used for this purpose:

https://www.bfarm.de/SharedDocs/Formulare/DE/Medizinprodukte/Meldeformular_Klinische-Pruef_SAE.html

All other SAEs for which a connection with the medical device under investigation, a reference product or the therapeutic or diagnostic measures applied in the clinical trial or the other conditions for conducting the clinical trial can be ruled out must be reported to the competent authority (BfArM) on a quarterly basis. The following form must be used for this purpose:

<http://ec.europa.eu/DocsRoom/documents/16477/attachments/2/translations>

If an SAE occurs in the context of a clinical study with a CE-certified medical device in which a connection with the test product cannot be ruled out, this must be reported immediately to the competent authority (BfArM) as an "incident" in accordance with Sections §3 and §5 MPSV as soon as it becomes known. If a serious undesirable event also constitutes an incident, the sponsor may also fulfil its obligation to report the incident by submitting an SAE report in accordance with §3 (5) MPSV. In the report it must be made clear that the obligation to report an incident in accordance with §3 (1) MPSV is also fulfilled.

Netherlands

The sponsor must immediately inform the Inspectorate (within two working days and not later than four calendar days) of SAEs which indicate an inevitable risk of death, serious injuries or serious illness, and requiring prompt remedial action for patients.

ottobock.	CLINICAL INVESTIGATION PLAN	Document number:	PD-PS00120016A-001
		Version number:	7
Project name	Clinical trial comparing C-Brace to KAFO/SCO	Project no.	PS00120016A

This includes SAEs that result in (temporary) suspension of inclusion of patients in the clinical investigation, discontinuation of the clinical investigation (temporarily or otherwise), or modification of the medical device.

Events that were reasonably foreseeable and are described as such in the Protocol and the patient information (“calculated risks”) are excluded from the above requirements, insofar as they do not lead to the (temporary) suspension or discontinuation of the clinical investigation or to modification of the medical device.

MEDDEV 2.7/3 stipulates that all other reportable events (see section 4 of MEDDEV 2.7/3) must be reported within no more than seven days. The Inspectorate applies a less intensive term in this respect. SAEs that do not fall under item 2 above may be reported quarterly in their totality to the Inspectorate by means of the reporting table, which can be found on the website of the European Commission.

Austria

The sponsor of a clinical investigation has to fully record all serious adverse events and notify them immediately to the BASG and to all other competent authorities in those member states of the EEA in which the clinical investigation is being performed.

Note:

- Where a medical condition is already established prior to the initiation of a clinical investigation and surgery has been scheduled to amend it, the definition of an adverse event according to MPG is not fulfilled and reporting to the BASG as SAE is not required. If the medical condition arises during the conduct of the clinical investigation, then SAE reporting to the BASG is required
- If a hospitalization preceded or was already planned prior to the initiation of a clinical investigation the definition of adverse event according to MPG is not fulfilled, no reporting as SAE is required. However, if unplanned hospitalization occurs during the conduct of the clinical investigation, SAE reporting to the BASG is required - whether or not causality has been established with the investigated device.

SAE and SADE that result in immediate risk of death, serious injury or illness will be reported without delay, at least within 2 calendar days to EK and BASG. All other SAEs and SADEs will be reported by sponsor within 7 days.

All incidents (Zwischenfall) will be reported by sponsor to competent authority (BASG) and ethics committee as specified in MPG §70(1) MPG.

ottobock.	CLINICAL INVESTIGATION PLAN	Document number:	PD-PS00120016A-001
		Version number:	7
Project name	Clinical trial comparing C-Brace to KAFO/SCO	Project no.	PS00120016A

13 Monitoring

The Clinical Project Manager will ensure proper monitoring of the study with special attention to verification of all clinical requirements, adherence to protocol, good clinical practices and compliance with applicable government and institutional regulations.

Authorized, qualified representatives of the sponsor or authorized, qualified staff of a CRO commissioned by the sponsor will visit the investigational site in regular intervals to verify the adherence to the clinical investigation plan and local legal requirements, to perform source data verification and to assist the investigator in his study related activities.

The monitor will at least document protocol deviations to informed consent procedures, SAE reporting within required timelines and investigational product handling in the Protocol Deviations Log. The Protocol Deviations Log will be consecutively completed during the ongoing trial as an appendix to the Monitoring Visit Report. Protocol deviations detected by data management should be notified to the sponsor and to the monitor. The monitor or the data management will notify the investigator of deviations in writing.

The following visits are planned: site qualification and feasibility, site initiation, routine visits and closeout visit. More details are given in the Monitoring Plan.

Monitor is responsible for reviewing the data for completeness and clarity. The details are provided in the Monitoring Plan. The investigator(s) commits to allowing audits to be performed by the sponsor and to potential inspections being performed by competent authorities. All data, documents and reports can be suspect to audits and regulatory inspections.

